9.3.3. Electrocardiogram

During the collection of ECGs, subjects should be in a quiet setting without distractions (eg, television, cell phones). Subjects should rest in a supine position for at least 5 minutes before ECG collection and should refrain from talking or moving arms or legs. If blood sampling or vital sign measurement is scheduled for the same time point as ECG recording, the procedures should be performed in the following order: ECG, vital signs, blood draw. A historical ECG within 1 day before signing of the ICF can be used in lieu of the baseline ECG requirement.

Twelve-lead ECGs will be recorded so that the different ECG intervals (PR, QRS, and QT) and heart rate will be measured. The QT intervals will be corrected for heart rate according to Bazett's (QTcB) and Fridericia's (QTcF) QT correction.^{5, 10}

Clinically relevant abnormalities occurring during the study should be recorded in the Adverse Event Section of the eCRF.

9.3.4. Vital Signs (temperature, pulse/heart rate, respiratory rate, blood pressure, blood oxygen saturation, level of consciousness)

Vital signs including temperature, pulse/heart rate, respiratory rate, blood pressure, peripheral arterial blood oxygenation, and level of consciousness will be assessed once daily at screening and at the Final Study Visit/Safety Follow-up Visit. Vital signs will be assessed at least 3 times daily until the subject is discharged from the hospital or until Day 14 (whichever comes first): in the morning (prior to study drug intake if applicable), approximately half-way in the middle of the day, and in the evening (prior to study drug intake if applicable). If the subject is discharged from the hospital, vital signs will be measured once daily on Day 5 and Day 10, if practically feasible. In case, per standard practice, vital signs are measured more frequently than required per protocol, these additional measurements will also be recorded in the eCRF.

Temperature will be measured orally.

Blood oxygen saturation will be measured using standard pulse oximeter. Subjects should have nail polish removed and should be encouraged to sit still during the measurements.

Blood pressure, pulse/heart rate, and respiratory rate measurements should be preceded by at least 5 minutes of rest in the supine position in a quiet setting without distractions (eg, television, cell phones).

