11.6. Efficacy Analyses

The efficacy endpoints will be analyzed on the Full Analysis Set, consisting of all subjects who were randomized, treated and had a confirmed influenza A infection, and will be analyzed by drug received.

Descriptive statistics will be used for all efficacy endpoints and will be tabulated by treatment arm and by age cohort. No formal statistical hypothesis testing will be made.

Clinical outcomes

The incidence of influenza complications will be categorized in a hierarchical fashion. The overall category will consist of any complication, consisting of the following subcategories:

- bacterial pneumonia (culture confirmed where possible),
- other bacterial superinfections,
- respiratory failure,
- pulmonary disease: asthma, chronic obstructive pulmonary disease [COPD]),
- cardiovascular and cerebrovascular disease (eg, myocardial infarction, congestive heart failure [CHF], arrhythmia, stroke),
- post-baseline ICU admission,
- all-cause mortality

The incidences on Day 28 of each (sub) category will be analyzed using logistic regression; baseline characteristics that are predictive of the incidence of complications can be included based on goodness of fit criteria. Odds ratios and associated 95% CIs will be reported of active vs. control treatment.

The time to improvement of vital signs is defined as the time from first study treatment to when at least 4 of 5 symptoms (temperature, blood oxygen saturation, heart rate, SBP, respiration rate) are recovered, including normalization of temperature and blood oxygen saturation. Normalization is defined in Table 6. If subjects satisfy these criteria at entry they will be censored at that time (effectively they will be excluded from the analysis). The data will be presented using a Kaplan-Meier curve. The time to event data will be modeled using the accelerated failure time (if the data provide an acceptable model fit) or alternatively a Cox proportional hazards model (in case the hazards are proportional). Additionally, the time to event data will be analyzed using the Gehan-Wilcoxon method.

Table 6: Resolution Criteria for Vital Signs

Assessment	Resolution Criterion
Temperature	≤ 37.2 °C or ≤ 37.8 °C rectal or tympanic
Oxygen saturation	$\geq 92\%$ on room air without supplemental oxygen
Respiration rate	≤ 24 /min
Heart rate	≤ 100 /min
Systolic blood pressure	≥ 90 mmHg

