4.2.1. Clinical Outcomes

▪ **Incidence of influenza complications**

The incidence of influenza complications from first intake up to Day 28 will be categorized in a hierarchical fashion. The overall category will consist of any complication, consisting of the following subcategories

- bacterial pneumonia (culture confirmed where possible),
- other bacterial superinfections,
- respiratory failure,
- pulmonary disease: asthma, chronic obstructive pulmonary disease [COPD]),
- cardiovascular and cerebrovascular disease (eg, myocardial infarction, congestive heart failure [CHF], arrhythmia, stroke),
- post-baseline ICU admission,
- all-cause mortality

The occurrence (yes/no) of influenza complications from first intake up to Day 28 of each (sub) category will be analyzed using logistic regression with treatment group as covariate. In case influenza complications occur in both age categories, age category will also be added as a covariate and as an interaction with treatment group. If the model will not fit the age category and it's interaction will be removed. Odds ratios and associated 95% CIs will be reported of active vs. control treatment and – if available – of elderly patients vs. patients < 65 years.

▪ **Time to improvement of vital signs**

The time to improvement of vital signs is defined as the time (in hours) from first study treatment until the first assessment (actual date and time) of a successive series of 3 recordings (over 4 scheduled successive analysis time points, 1 missing time point is allowed) where at least 4 of 5 symptoms (temperature, blood oxygen saturation, heart rate, SBP, respiration rate) are recovered, with at least normalization of temperature and blood oxygen saturation. Normalization is defined in Table 6. If subjects satisfy these criteria at entry they will be censored at that time.

Only vital signs assessments assessed during hospitalization and up to Day 14 (during hospitalization) will be taken into account to determine time to improvement of vital signs. Assessments taken after hospital discharge or after day 14, whichever, comes first will not be taken into account. In case, there was more than one hospitalization period, only assessments of the first hospitalization period will be used.

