In cases where there are no sufficient recordings of clinical stability as defined above, the endpoint will be censored. Censoring will be at the first time of clinical stability, if and only if after this observation there is no recording of non-resolved influenza symptoms (ignoring missing recordings). If there are no recordings of resolved symptoms satisfying this criterion, the time of censoring is the first possible time point an assessment could have been done after the last observation of vital signs recordings, which is 13:00 on the same day if the last observation was a morning assessment (from 3:01 until 11:00), 21:00 if the last observation was an afternoon assessment (from 11:01 until 19:00), 5:00 the next day if the last assessment was an evening assessment (from 19:01 until 03:00). There are two exceptions: in case the last available vital signs record is on the day of discharge in the evening or on day 14 during hospitalization in the evening. If at this record (last record for the subject to be taken into account for time to clinical stability) there is no clinical stability, the time of the last assessment (day of discharge, evening or day 14, evening) will be taken as the time of censoring.

The data will be presented using a Kaplan-Meier curve and Kaplan-Meier estimates by treatment group, overall and by age group. The time to event data will be modeled using the accelerated failure time model. The model will use the parametric shape, selected based on the goodness of fit criterion (AIC), and may take a Weibull, log-logistic, lognormal, or gamma distribution. Age category, NEW Score at baseline and treatment group will be included as covariates. If the data don't provide an acceptable model fit, alternatively a Cox proportional hazards model can be used (in case the hazards are proportional). In case a Cox proportional hazards model is used a Log-log plot of survival will be added to check the proportional hazard assumption. Additionally, the time to event data will be analyzed using the logrank test and the Gehan-Wilcoxon method.

Table 6: Resolution Criteria for Vital Signs

Assessment	Resolution Criterion
Temperature	Oral temperature ≤ 36.5 °C for elderly and ≤ 37.2 °C for adults
Oxygen saturation	$\geq 92\%$ on room air without supplemental oxygen*
Respiration rate	≤ 24 /min
Heart rate	≤ 100 /min
Systolic blood pressure	≥ 90 mmHg

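### Time to vital-sign and respiratory improvement censors patients discharged after only one or two normal recordings at their recovery time, so the censoring is informative and median times are biased upward

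*SAP*

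**What the plan says.** Protocol 11.6 defines time to improvement of vital signs as "the time from first study treatment to when at least 4 of 5 symptoms" have recovered, with temperature and oxygen saturation among them. It asks for no confirmation and sets no in-hospital limit.

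SAP 4.2.1 narrows this in three ways.

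- The event is the first of a "successive series of 3 recordings (over 4 scheduled successive analysis time points, 1 missing time point is allowed").
- The data are restricted: "Only vital signs assessments assessed during hospitalization and up to Day 14 (during hospitalization) will be taken into account". The SAP then repeats the limit from the other side: "Assessments taken after hospital discharge or after day 14, whichever, comes first will not be taken into account". Only the first hospitalization counts.
- On shortfalls: "In cases where there are no sufficient recordings of clinical stability as defined above, the endpoint will be censored". The time is then fixed: "Censoring will be at the first time of clinical stability, if and only if after this observation there is no recording" of unresolved status. The SAP's wording here refers to influenza symptoms. I read it as a later recording that fails the vital-sign criteria, since both documents call the five vital signs symptoms.

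Time to improvement of respiratory status takes the same three-recording definition and an analogous analysis. Both endpoints go to Kaplan-Meier and an accelerated failure time model, with Cox as the fallback, plus logrank and Gehan-Wilcoxon. No sensitivity analysis is given for discharge. SAP 1.6, which lists changes to the planned analysis, names only the temperature criterion for this endpoint.

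**The concern.** All the planned methods assume that a patient censored at time t has the same future chance of the event as others still at risk at t. Here the patient is censored at t because the criteria were first met at t and discharge came before the run of three could be completed. Kaplan-Meier then treats a recovered patient as one who might have gone on much longer without recovering. The survival curve stays too high and the median is too long.

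Discharge normally follows stability, so this is likely to be common. Time to hospital discharge is itself a secondary outcome on which the arms may differ. If the stay after recovery also differs by arm, the rule would remove more events from the arm that goes home sooner.

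**Working it through.** The documents give no expected median, event count or power for these endpoints, so there is no planned figure to reproduce. I checked the timing arithmetic and then simulated the rule.

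**How long a run of three takes.** In hospital, "Vital signs will be assessed at least 3 times daily until the subject is discharged from the hospital or until Day 14" (Protocol 9.3.4). The SAP's nominal censoring slots are 5:00, 13:00 and 21:00, which are 8 h apart.

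- First to third recording: 2 × 8 = 16 h.
- With one missing time point: 3 × 8 = 24 h.
- Morning and evening recordings precede dosing. With the SAP's imputed intake times of 8:00 and 20:00, a run that starts in the morning finishes in 12 h.

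A patient discharged sooner than this after the first normal recording cannot be an event.

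**What happens under the rule.**

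| In-hospital recordings | Treatment in the SAP |
|---|---|
| Three normal in the run | Event at the first normal one |
| One or two normal, none abnormal after, then discharge | Censored at the first normal one |
| None normal before discharge | Censored, normally at the next possible slot |

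The first two rows carry the same time and differ only in the event flag. What sets the flag is how soon discharge followed.

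**Simulated size.** My assumptions: everyone recovers; recovery time T is lognormal with median 48 h and log-SD 0.7; discharge is at T + L; recordings are every 8 h; the first normal recording is at f = 8 × ceil(T/8); the number of normal recordings is k = floor((T + L − f)/8) + 1, or 0 if discharge precedes f; an event needs k ≥ 3. The lag L is either exponential or a less skewed gamma with shape 4.

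| Lag shape | Mean lag (h) | Events | Censored with 1–2 normal | None normal before discharge | Kaplan-Meier median (h) |
|---|---|---|---|---|---|
| Exponential | 18 | 33% | 48% | 19% | 120 |
| Exponential | 24 | 44% | 41% | 15% | 96 |
| Exponential | 36 | 57% | 32% | 11% | 72 |
| Exponential | 48 | 66% | 26% | 8% | 72 |
| Gamma | 18 | 36% | 61% | 3% | 112 |
| Gamma | 24 | 57% | 41% | 1% | 72 |
| Gamma | 36 | 81% | 18% | 1% | 56 |
| Gamma | 48 | 91% | 9% | <1% | 56 |

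If discharge while normal completes the run, the median is about 56 h. It falls on 48 or 56 h because the true 48 h lies on a grid point.

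**Treatment comparison.** Recovery medians are 36 h (active) and 48 h (control), so the true time ratio is 36/48 = 0.75. The model is a Weibull accelerated failure time model with exponential lags.

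| Mean lag, active vs control (h) | Ratio, SAP rule | Ratio, discharge completes the run |
|---|---|---|
| 24 vs 24 | 0.77 | 0.77 |
| 36 vs 48 | 0.83 | 0.78 |
| 24 vs 36 | 0.91 | 0.79 |
| 18 vs 30 | 1.01 | 0.81 |

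Simulation noise is about 0.02. The 0.77 in place of 0.75 is mostly the recording grid, which adds about 4 h to each arm: (36 + 4)/(48 + 4) = 0.77.

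**The case against.** - **The size rests on an input the documents do not give.** This stands. With a less skewed lag averaging 36 h or more, the median is barely affected and 9% to 18% of patients are lost as events.
- **A reader might infer that the fastest recoveries are lost.** The rule does not do that. Loss depends on the time from first normal recording to discharge, not from first dose. A patient normal at 16 h who stays another day is an event; one normal at 100 h who leaves 8 h later is censored. The affected patients are also censored, not excluded.
- **A reader might infer that the comparison is biased against active treatment.** That follows only if active patients have a shorter stay after recovery. Nothing in the documents shows this, and a drug that speeds recovery need not shorten the stay that follows it. With equal lags the ratio is unaffected.
- **Confirmation is reasonable.** Requiring sustained normal signs guards against transient normalization, and Protocol 11 leaves detail to the SAP. I accept this. The fault is in how an incomplete run is handled at discharge.
- **Dropping post-discharge recordings is not the cause.** After discharge the protocol has only single measurements on Days 5, 10 and 28, so admitting them would not complete the run.
- **The stakes are limited.** These are two secondary endpoints in an exploratory study without formal testing, and time to discharge and the Day 8 ordinal scale capture earlier discharge directly. That limits the consequence but does not make the estimates right.

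The SAP handles the same situation differently for viral negativity (4.2.2): a first negative that is the last available result counts as an event. The diary endpoints use censoring wording like that for vital signs, but diaries continue after discharge, so discharge does not cut their runs short.

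**Conclusion.** The point holds for both endpoints. For patients discharged with one or two normal recordings and none abnormal afterwards, the censoring time is the recovery time, so independent censoring fails by construction. Events are lost and Kaplan-Meier medians are pushed upward.

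Under the assumed 48 h recovery median and mean lags of 18 to 48 h, the effect runs from minor (9% censored this way, median essentially right) to large (61% censored this way with the gamma lag; a median of 120 h with the exponential lag). With the maximum of 90 subjects, and if all recover, that is about 0.09 × 90 = 8 to 0.61 × 90 = 55 patients.

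Bias in the treatment ratio is conditional. It is absent with equal lags and runs against the arm that leaves sooner after recovery when lags differ: a true 0.75 is estimated as 0.83, 0.91 or 1.01 in the three cases examined. No significance level or power figure is affected.

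**What to change.** In SAP 4.2.1, for both vital signs and respiratory status:

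1. For subjects discharged alive in whom every recording from the first normal one to discharge meets the criteria, count the event at that first normal recording. Keep the three-recording rule for subjects still in hospital.
2. Report this and the current rule, one as the sensitivity analysis of the other.
3. Tabulate by arm the subjects discharged with only one or two normal recordings. This shows directly whether the lag differs between arms.
4. In SAP 1.6, list the three-recording requirement and the in-hospital restriction as departures from the Protocol 11.6 definition.

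The cost is SAP wording and a derivation change on data already collected. There are two downsides. Discharge with normal signs is taken as sustained recovery on fewer recordings than are asked of inpatients, so discharge practice enters the definition; reporting both rules makes that visible. Subjects discharged before any normal recording also remain censored, so some bias is left: with lags of 18 vs 30 h the ratio is 0.81, not 0.77.
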